6.1 Summary of Patient Disposition

Patient disposition in the open label-treatment period will be summarised by lead-in study and in total, and include the number of patients in each analysis set defined for the period, and the number of patients in the APTS who completed or withdrew from treatment. The corresponding summary will be generated for the open-label treatment period with memantine for the total study.

6.2 Withdrawal

The number of patients who withdrew from the open-label treatment period will be summarised by primary reason for withdrawal as well as by all reasons for withdrawal.. Similar summaries will be created for the open-label treatment period with memantine. The summaries will also be presented by lead-in study for the open-label treatment period.

Patients who withdrew from treatment during the open-label treatment period will be listed and the listing will include the number of days on idalopirdine in the open-label treatment period, the primary reason for withdrawal from treatment, and all reasons for withdrawal from treatment. A similar listing will be created for patients who withdrew from treatment during the open-label treatment period with memantine.

7 Demographics and Other Baseline Characteristics

Demographics and baseline characteristics at Baseline I will be summarised for patients in the APTS and the APTS2.

Demographics (sex, age, ethnicity, and race), patient characteristics (weight, height, BMI), and efficacy variables at Baseline I will be summarised.

Past and concurrent medical, neurological, and psychiatric disorders at the lead-in study Screening Visit (coded using the Medical Dictionary for Regulatory Activities [MedDRA], Version 19.0 or later), will be summarised.

The summaries will also be presented by lead-in study for the APTS.

LU Study Number: 14861B Trial Site Number: Study Level Pluto ID: CLI 00933680

8 Recent and Concomitant Medication

Recent and concomitant medication will be coded using the WHO Drug Dictionary (WHO-DDE), version WHO ATC MAR16., and summarised by anatomical therapeutic chemical (ATC) code, and generic drug name.

For the open label treatment period summaries will be prepared for:

- Concomitant medication continued after Baseline II
- concomitant medication started after Baseline II and at or before Baseline III for patients in APES2

For the open label treatment period with memantine summaries will be prepared for;

- concomitant medication continued after Baseline III
- concomitant medication started after Baseline III

A listing will be created that includes information about memantine dosages over the course of the open label treatment period with memantine.

9 Exposure

Exposure to IMP in this study will be defined as: date of last dose of IMP – date of first dose of IMP + 1

For details about handling of missing IMP start or stop date, see section 18.4.1 (IMP start and stop date)

Exposure to IMP in each treatment period will be summarised using descriptive statistics, and include the patient years of exposure (PYE). PYE will be calculated as the sum of the number of days of exposure to IMP for each patient, divided by 365.25 days.

In addition, exposure to IMP in each treatment period will be categorised into day intervals. The intervals for the open-label treatment period are the following: $(1-28\ [0-1\ month], 29-56\ [1-2\ months], 57-84\ [2-3\ months], 85-126\ [3-4.5\ months], 127-168\ [4.5-6\ months], 169-252\ [6-9\ months].$ The intervals for the open-label treatment period with memantine are the following: $(1-168\ [0-6\ months], 169-252\ [6-9\ months], 253-364\ [9-12\ months], 365-448\ [12-15\ months])$. Missing values of exposure will not be imputed.

Number and percentage of patients with dose reduction of IMP to 30 mg/day in the open-label treatment period will be summarised. The mean dose of IMP will be calculated for each patient and summarised (mean, median, and lower and upper quartiles). Categorical summaries of patients' dosage at each visit will be presented as well.

LU Study Number: 14861B Trial Site Number: Study Level Pluto ID: CLI 00933680

10 Efficacy

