16.6 Recent and Concomitant Medication

Recent and concomitant medication in each treatment period will be summarised by anatomical therapeutic chemical (ATC) code and generic drug name by treatment group (placebo or idalopirdine all doses pooled) in the lead-in study and in total.

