Antipsychotics atypical	Only treatment with risperidone (maximum 2 mg/day) or quetiapine (maximum 100 mg/day) is allowed if absolutely necessary, and if prescribed according to treatment guidelines. Risperidone or quetiapine treatment should not be initiated within 3 days of a study visit with efficacy assessments.
Antiviral agents	Anti-HIV agents are disallowed.
Anxiolytics	The use of benzodiazepines as anxiolytic treatment is acceptable, provided the
	dose remains fixed during the study. Where absolutely necessary,
	benzodiazepine treatment can be initiated as a short-term anxiolytic treatment
	during the study, as long as the treatment is not initiated within 3 days of a
	study visit with efficacy assessments.
	Use of antidepressants is described in the corresponding row.
Benign prostate hyperplasia	Only alpha-1 blockers (Terazosin, Tamsulosin, Doxazosin) and finasteride are
Beta-blockers	Precaution should be taken when administering betablockers
Cough/cold agents	Onen-label treatment period (initial 28-week period):
Cough cold ugents	Only non-opioids and codeine allowed.
Diuretics	Open-label treatment period with memantine (substudy): Only non-opioids and codeine allowed. Dextromethorphan disallowed. Open-label treatment period with memantine (substudy): Hydrochlorothiazide and triamterene are disallowed.

Drug Class	Details		
H2 blocker/proton pump	Open-label treatment period (initial 28-week period):		
inhibitors	Dose modifications and initiation of treatment allowed during the study.		
	Open-label treatment period with memantine (substudy):		
	Dose modifications and initiation of treatment allowed during the study, but		
TT ' 1 1' 1	caution should be exercised according to the memantine SmPC.		
Hormones, including hormone-	Dose modifications and initiation of treatment allowed during the study.		
replacement therapy	Steroids: See separate row.		
Hormone suppressants	Dose modifications and initiation of treatment allowed during the study.		
Insulin	Rosiglitazone is disallowed.		
Hypolipidaemics	Dose modifications and initiation of treatment allowed during the study.		
Muscle relaxants	Allowed on a p.r.n. basis (not to exceed 5 consecutive days).		
	As specified in Section 4.5 of the donepezil, rivastigmine and galantamine		
	SmPC precaution should be taken when administering neuro-muscular		
	blockers.		
NMDA-antagonist (memantine)	Open-label treatment period (initial 28-week period):		
	Disallowed during the study.		

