1.3 Other Objectives

Open-label treatment period with memantine (sub-study):

To explore population pharmacokinetics.

2 Study Design

This is an interventional, multi-national, multi-site, open-label extension study in patients with mild to moderate AD who completed the 24-week "lead-in" double-blind, placebo controlled clinical studies 14861A and 14862A (from now on these studies will be referred to as "lead-in study" in the document). Randomized, blinded treatment in lead-in study will remain blinded to sites, CRAs, patients, and investigators until patients have completed the extension study (the sponsor will generally be un-blinded after unblinding of 14861A and 14862A occurs).

LU Study Number: 14861B Trial Site Number: Study Level Pluto ID: CLI 00933680

[figure not shown]
Patients completing the open-label treatment period and who will not continue into the 24-week open-label memantine sub-study (described below) will enter a 4-week safety follow-up period. Thus the total study duration of the open-label treatment period per patient from Baseline II (Visit 1 of the open-label treatment period and Visit 7 of the lead-in study) to the end of the follow-up will be approximately 32 weeks.

Some sites will be participating in the open-label treatment period with memantine (substudy). In total, 100 patients who have completed the open-label treatment period will be recruited for the for the memantine sub-study. For these patients, the study will include two consecutive periods:

- Open-label treatment period (initial 28-week period): 28-weeks with idalopirdine 60 mg/day as adjunctive treatment to donepezil (10 mg/day). The dose of idalopirdine can be decreased to 30 mg/day if 60 mg/day is not well tolerated in the opinion of the investigator. The Baseline Visit of this period (Baseline II) will be the same visit as Visit 7 (Completion Visit) in the lead-in studies.

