• Adverse events (AEs)

LU Study Number: 14861B Trial Site Number: Study Level Pluto ID: CLI 00933680

- Clinical safety laboratory tests
- Vital signs
- Weight
- Electrocardiograms (ECGs)
- Columbia Suicide Severity Rating Scale (C-SSRS)

Other endpoints

• Plasma concentrations of idalopirdine and memantine in the open label treatment period with memantine

4 Analysis Sets

The following analysis set will be used to analyse and present data:

The sets of patients to be analysed are defined as follows:

Open label treatment period

- all-patients-enrolled set (APES) all patients enrolled in the open-label treatment period
- *all-patients-treated set* (APTS) all patients in APES who took at least one dose of IMP in the open-label treatment period

Open label treatment period with memantine

- *all-patients-enrolled set 2* (APES2) all patients who enrolled in the open-label treatment period with memantine
- *all-patients-treated set 2* (APTS2) all patients in APES2 who took at least one dose of IMP or memantine in the open-label treatment period with memantine.

Each patient will be classified according to these definitions based on information in data, and no Classification Meeting will be held.

If not otherwise specified, tables, figures, and listings will be based on the APTS for the open-label treatment period, and on APTS2 for the open-label treatment period with memantine.

5 Descriptive Statistics

Unless otherwise specified, summary statistics (n, arithmetic mean, standard deviation [SD], median, lower and upper quartiles, minimum and maximum values) will be presented for continuous variables, and counts and, if relevant, percentages will be presented for categorical variables.

Tables and figures for the open label treatment period will be presented by lead-in treatment group and in total.

LU Study Number: 14861B Trial Site Number: Study Level Pluto ID: CLI 00933680

Unless otherwise specified, data listings will include lead-in treatment group (placebo or idalopirdine [dose 10mg, 30mg, or 60mg]), site, patient screening number (from lead-in study), and lead-in study-Baseline I information on sex, age, race, and weight.

6 Patient Disposition

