11.1.4 Allocation of TEAEs to Treatment Periods

TEAEs will be allocated to treatment periods according to the time of onset of the adverse event:

• *adverse event in the open-label treatment period* – an adverse event that starts or increases in intensity after the date of Baseline II and at or before the date of the last protocol-

LU Study Number: 14861B Trial Site Number: Study Level Pluto ID: CLI 00933680

- specified contact in the study for patients not continuing into the open-label treatment period with memantine, and at or before the date of Baseline III for patients in the APES2.
- adverse event in the open-label treatment period with memantine an adverse event that starts or increases in intensity after the date of Baseline III and at or before the date of the last protocol-specified contact in the study.

Note, the completion Visit in the lead-in studies are the same as the Baseline II Visit in the extension study, and adverse events ongoing or starting at Baseline II and not increasing intensity will only be reported in the lead-in study.

All tables and listings will be presented separately for adverse events in the open label treatment period, and the open label treatment period with memantine.

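### As worded, SAP section 8 limits the 28-week table of newly started medication to the planned 100 memantine-substudy patients, although the clause was probably meant only as an end date

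*SAP*

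**What the plan says.** SAP section 8 lists two summaries for the 28-week period. The first is "Concomitant medication continued after Baseline II", with no population named. The second is "concomitant medication started after Baseline II and at or before Baseline III for patients in APES2". No other bullet covers drugs started in that period.

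SAP section 4 defines APES2 as "all patients who enrolled in the open-label treatment period with memantine". SAP section 2 gives its planned size: "In total, 100 patients who have completed the open-label treatment period will be recruited". The default set is also in section 4: "If not otherwise specified, tables, figures, and listings will be based on the APTS for the open-label treatment period".

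Protocol section 16.6 makes a wider commitment: "Recent and concomitant medication in each treatment period will be summarised by anatomical therapeutic chemical (ATC) code" and generic drug name, by lead-in treatment group and in total. Protocol section 16.2 puts all descriptive statistics for the 28-week period on the APTS. SAP section 17, which lists departures from the protocol, names only the change to the C-SSRS summary.

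**The concern.** The bullet for newly started drugs names a set, so the APTS default, which applies only where nothing else is specified, does not clearly override it. A programmer following the sentence could build the table on APES2 alone. That would be a narrower analysis than the protocol describes, with no declaration of the change.

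Protocol Appendix II allows some psychotropic drugs to be started during the study: risperidone or quetiapine, short-term benzodiazepines and certain hypnotics. It also restricts the timing, for example "Risperidone or quetiapine treatment should not be initiated within 3 days of a study visit with efficacy assessments", so the plan itself treats new starts as relevant to the ratings. A description of which drugs were added is part of the background to a 28-week safety and disease-course report.

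APES2 could not stand in for the remaining patients. Under Protocol sections 5.1 and 5.3 it requires completion of Visit 6, an MMSE score of at most 19 and an investigator's judgement that memantine is needed, at selected sites in 13 countries. By construction it contains nobody who withdrew during the 28 weeks.

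**Working it through.** **Step 1: the two rules side by side.** The adverse event rule in SAP section 11.1.4 and the medication bullet in SAP section 8 divide the same period.

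| | Adverse events (SAP 11.1.4) | Newly started medication (SAP 8) |
|---|---|---|
| Start | After Baseline II | After Baseline II |
| End, patients not entering the substudy | Last protocol-specified contact | Not stated |
| End, patients in APES2 | Baseline III | Baseline III |

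Section 11.1.4 ends the period at the last protocol-"specified contact in the study for patients not continuing into the open-label treatment period with memantine, and at or before the date of Baseline III" for APES2. There, APES2 qualifies only the second end date. Section 8 keeps the second branch in almost the same words and lacks the first. Two readings follow:

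- *Restriction*: APES2 is the population of the table.
- *End date*: APES2 limits only the Baseline III cut-off, and the table covers the APTS.

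**Step 2: the plan's own figure.** Inputs from Protocol section 16.11 and SAP section 15 are three arms of 310, three arms of 280, 85% lead-in completion, and 85% of those eligible and completing the extension.

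- Maximum: 3 × 310 + 3 × 280 = 1,770
- Expected lead-in completers: 1,770 × 0.85 = 1,504.5
- Expected extension completers: 1,504.5 × 0.85 = 1,278.8, which agrees with the stated figure of about 1,280

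**Step 3: share of patients outside APES2, with APES2 = 100.** The formula is 1 − 100/N.

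| Denominator N | 100/N | Outside APES2 |
|---|---|---|
| 1,278.8 (extension completers) | 7.8% | 92.2% |
| 1,504.5 (lead-in completers) | 6.6% | 93.4% |
| 1,770 (maximum) | 5.6% | 94.4% |

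The documents do not state the expected size of the APTS, so the result is given as a range. Under the restriction reading, new starts in 92.2% to 94.4% of patients are untabulated. Under the end-date reading the share left out is 0%.

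**The case against.** The strongest reply is that no restriction was intended.

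- Section 11.1.4 uses nearly the same words purely as a cut-off.
- An author limiting a table to treated substudy patients would more naturally have named APTS2, the SAP's default set for substudy tables.
- Section 8 opens by promising a medication summary without restriction, and its companion bullet names no set.
- The silence of section 17 fits an author who saw no change to declare.

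This stands as evidence of intent, and it makes the end-date reading the more plausible one. It does not repair the sentence, which still supports the other reading.

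A second reply is that the missing end date is harmless, because non-continuing patients have no later treatment period and every drug they start after Baseline II belongs here. The substudy bullet for drugs started after Baseline III has no end date either. This largely stands. One choice is left open: the flow chart in SAP Appendix II also records concomitant medication at Visit 7, so the sentence should say whether starts during follow-up count.

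A third reply is that the practical loss is limited. Drugs continued after Baseline II are summarised for the whole APTS. Protocol section 7 requires an adverse event record when a drug is started for a new or worsening disorder, and adverse events are tabulated on the APTS. This also stands, although an adverse event table does not show which drugs were added.

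A reader might infer that about 93% of patients start a drug. The documents give no rate of new starts; the figure is only the share of patients outside APES2. A reader might also infer that a corrected table would show how far NPI or ADAS-Cog results reflect added treatment. A frequency table by ATC code and generic name carries no timing and no link to scores, so it could not show that. Nor do the documents promise subtotals by drug class, so their absence is not a fault.

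**Conclusion.** The point holds as a defect of wording. Read literally, the only 28-week summary of newly started medication covers the planned 100 substudy patients and omits new starts in roughly 92% to 94% of patients. That conflicts with Protocol sections 16.6 and 16.2 and is not declared in SAP section 17. The range rests on the planned APES2 size of 100 and on the plan's 85% assumptions, with the 1,770 maximum as the upper denominator.

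It would go too far to say that the sponsor decided to leave these patients out. The parallel in section 11.1.4 points to a dropped branch, and under that reading no patient is omitted. Data collection is unaffected either way. What needs correcting is a stated rule that, followed as written, yields a table omitting most of the study.

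**What to change.** Reword the second 28-week bullet of SAP section 8 on the APTS, with both end dates from section 11.1.4. In substance: *medication begun after Baseline II, counted up to the last protocol-specified contact in patients who do not go on to the memantine period, and up to Baseline III in patients in APES2*. The first end date includes the follow-up period, as it does for adverse events. A table footnote can say so.

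If a restriction to APES2 is intended, keep it but declare it in SAP section 17 as a departure from Protocol sections 16.6 and 16.2, with the reason.

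The cost is one SAP sentence. The data are already collected, and the only programming effect is on the population and the end date of one table.

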10.1 General Efficacy Analysis Methodology

All analyses will be performed by lead-in study.

For the open label treatment period, absolute scores, change from Baseline I scores, and change from Baseline II scores for the efficacy variables will be summarised by visit week. The summaries of absolute scores and change from Baseline I scores will include data from the lead-in study and the open-label treatment period.

For the open label treatment period with memantine, absolute score and change from Baseline Baseline III in MMSE total score will be summarised by visit week.

All the p-values will be based on two-sided tests; the confidence intervals (CIs) will be two-sided.

Nominal p-values will be presented together with nominal 95% CIs.

10.2 Exploratory Analysis of Efficacy

Changes from baseline I in ADAS-Cog total score, ADCS-ADL₂₃ total score, NPI total score, NPI individual items, and MMSE total score will be analysed using a restricted maximum likelihood (REML)-based mixed model for repeated measures (MMRM) approach. Baseline will be defined as the baseline in the lead-in study (Baseline I). The model will include data from visits in both the lead-in study and the open label treatment period. The model will include the fixed categorical effects of treatment group in the lead-in study, country, visit week, treatment-by-week interaction, MMSE-stratum ($<19, \ge19$) at baseline I, and MMSE-stratum at baseline I-by-visit interaction and the continuous covariates of baseline score and baseline score-by-visit interaction.

In all analyses, an unstructured covariance structure will be used to model the within-patient errors. The Kenward-Roger approximation will be used to estimate denominator degrees of freedom. The analysis will be based on the missing-at-random (MAR) assumption and performed using all available observations (observed cases [OC] data).

Line plots will be created to illustrate the MMRM estimates of least squares means by visit week. ADCS-CGIC will be analysed using the same methodology, using the scores at each visit and the ADCS-CGIC score at Baseline I in the lead-in study as baseline.

LU Study Number: 14861B Trial Site Number: Study Level Pluto ID: CLI 00933680

11 Safety

11.1 Adverse Events

11.1.1 General Methodology for Adverse Events

The tables for the open label treatment periodwill be sorted in descending order by the percentage of patients in the lead-in IDL 60 mg group. Unless otherwise specified, the summaries of adverse events will include the total number and percentage of patients with an adverse event. For sex-specific preferred terms, the denominator in the % calculations will be the number of patients of that sex. Sex-specific preferred terms will be marked in the summaries.

In summaries of adverse events presented by intensity, the maximum intensity of the adverse event in the treatment period will be used for patients who have more than one intensity of that event. Adverse events for which information on intensity is missing will be classified as *severe*.

Listings of adverse events will be sorted by lead-in study treatment group, site, patient screening number (from lead-in study), and adverse event start date and include preferred term, investigator term, adverse event start date, days since first dose of IMP in the treatment period, duration of the adverse event in the treatment period, date of death, action taken, causality, intensity, seriousness, and outcome. For adverse events that change in intensity, each intensity will be included.

11.1.2 Coding of Adverse Events

Adverse events will be coded using MedDRA, Version 19.0, or later.

11.1.3 Classification of Adverse Events

Adverse events will be classified according to the time of onset of the adverse event: treatment-emergent adverse event (TEAE) – an adverse event that starts or increases in intensity after the date of Baseline II.

An adverse event is considered causally related to the use of the IMP when the causality assessment by the investigator is *probable* or *possible*.

